3.1.3.4 Dose Adjustment for Venetoclax

In the ramp-up period, the dose of venetoclax should be adjusted according to the concomitant medication used by the patient, as outlined in Table 3.

The following dose modification rules in Table 7 and Table 8 should be followed in the event of each toxicity related to venetoclax during the study.

Table 7 Venetoclax Dose Modification for Toxicities

Tumor Lysis Syndrome

Study Number: ONO-7475-01 Protocol	Version: 10.0 [incorporating Amendments #1–9]
---------------------------------------	---

Event	Occurrence	Action
Blood chemistry changes or symptoms suggestive of tumor lysis syndrome (TLS)	Any	Withhold the next day's dose. If resolved within 24 to 48 hours of last dose, resume at the same dose.
		For any blood chemistry changes requiring more than 48 hours to resolve, resume at a reduced dose (see Table 8).
		For any events of clinical TLS, resume at a reduced dose following resolution.
Non-Hematologic Toxicities		
Grade 3 or Grade 4 nonhematologic toxicities	First occurrence	Interrupt venetoclax. For the event of infection, monitor patients closely for signs and symptoms of infection and treat promptly. Venetoclax may be resumed at the same dose once the toxicity has resolved to Grade 1 or baseline level. No dose modification is required.
	Second and subsequent occurrences	Interrupt venetoclax. For the event of infection, monitor patients closely for signs and symptoms of infection and treat promptly. Follow dose reduction guidelines in Table 8 when resuming treatment with venetoclax after resolution. A larger dose reduction may occur at the discretion of the Investigator.
Hematologic Toxicities		
Grade 4 neutropenia with or without fever or infection; or Grade 4 thrombocytopenia	Occurrence prior to achieving remission	Transfuse blood products, administer prophylactic and treatment anti-infectives as clinically indicated. [REDACTED]
	First occurrence after achieving remission and lasting at least 7 days	Monitor blood counts. Administer granulocyte-colony stimulating factor (G-CSF) if clinically indicated for neutropenia. [REDACTED]

[figure not shown]
	Subsequent occurrences in cycles after achieving remission and lasting 7 days or longer	Monitor blood counts. Administer G-CSF if clinically indicated for neutropenia.
--	---	---

Table 8 Venetoclax Dose Reduction for Toxicity

Dose at Interruption (mg)	Restart Dose (mg)
400	300
300	200
200	100
100	50
50	20
20	10

[figure not shown]

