9.1.2 Adverse Event Relationship to Investigational Product(s)

The Investigator must classify the relationship of the AE to ONO-7475 (both Parts) and venetoclax (Part D only).

The possible relationships for Part A are:

- | | |
|----------------------------------|--|
| Not related/
unlikely related | The temporal sequence between the AE and drug administration is such that the drug is not likely to have had any reasonable association with the observed event; or underlying disease, other drugs or chemicals provide plausible explanations. |
| Possibly related | 
The AE follows a reasonable time relationship from drug administration;
 
and
 
The AE could also be explained by concurrent disease or other drugs or chemicals.
 
Note: Information on drug withdrawal may be lacking or unclear.
 |
| Probably related | 
The AE follows a reasonable time relationship from drug administration;
 
The AE is unlikely to be attributed to concurrent disease or other drugs or chemicals;
 
and
 
Follows a clinically reasonable response upon withdrawal (dechallenge);
 
Note: rechallenge positive data are not required to fulfill this definition.
 |
| Definitely related | 
The AE follows a reasonable time relationship from drug administration (i.e., occurs in a plausible time relationship to drug administration);
 
The AE cannot be explained by concurrent disease or other drugs or chemicals;
 |

The AE abates or follows a clinically reasonable response upon withdrawal (dechallenge positive);

and

The AE is confirmed by reappearance of the reaction on repeat exposure (rechallenge positive).

The possible relationships for Part D are:

- | | |
|-------------|---|
| Not related | The temporal sequence between the AE and drug administration is such that the drug is not likely to have had any reasonable association with the observed event; or underlying disease, other drugs or chemicals provide plausible explanations. |
| Related | 
The AE follows a reasonable time relationship from drug administration (i.e. occurs in a plausible time relationship to drug administration);
 
The AE cannot be explained by concurrent disease or other drugs or chemicals;
 
The AE abates or follows a clinically reasonable response upon withdrawal (dechallenge positive);
 
or
 
The AE is confirmed by reappearance of the reaction on repeat exposure (rechallenge positive).
 |

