9.2.2 Serious Adverse Event Reporting by the Investigator or Designee

All SAEs, regardless of suspected relationship to study drug, must be reported by the Investigator or their authorized designee to designated service provider immediately, and in no case later than 24 hours, following knowledge of the SAE.

All SAEs are documented in the SAE form and reported electronically through the designated service provider's electronic data capture (EDC) system.

If the event meets serious criteria and it is not possible to access the EDC system, the Investigator or their authorized designee should contact the designated service provider, either by e-mail or telephone, and fax the completed paper SAE form to the designated service provider within 24 hours of awareness. The SAE

information must be entered into the EDC system within 24 hours of the system becoming available.

Safety Contact Information

[REDACTED]

[REDACTED]

[REDACTED]

[REDACTED]

[REDACTED]

The initial report of an SAE must not be delayed by the investigational site beyond 24 hours in order to collect additional information. Any medical information relevant to the reported SAE which becomes available to the investigational site staff following the initial SAE report should be reported to designated service provider as part of a follow-up SAE report. The reporting procedure should be referred to the outlined above for initial reporting of SAEs. Medical records transmitted as part of the SAE report must not disclose study patients' personal data, such as patient name, any contact information, name of patients' relatives, etc. The study patient is to be identified by the unique study-specific subject number only.

As for AEs, SAEs will be collected from the time informed consent is given until the follow-up visit, or until voluntary withdrawal of a clinical study patients' consent (refer to Section 8.3). SAEs that occur after the SAE reporting period and that are considered related to study drug will be reported to the Sponsor, if the Investigator becomes aware of them.

Unless they withdraw consent for further follow-up, patients who discontinue study therapy will be followed for acquisition of safety information through 30 days after the last dose of study treatment (or initiation of new anti-cancer therapy, whichever occurs first), and for collection of information regarding survival.

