9.2.3 Serious Adverse Event Processing and Reporting by the Study Sponsor or Designee

All SAEs will be processed by the study Sponsor or contracted designee according to study-specific SAE processing guidelines.

The Sponsor, or contracted designee, will be responsible for submitting suspected, unexpected, serious adverse reactions (SUSARs) involving the study drug to the applicable regulatory authorities according to ICH guidelines and applicable regulations. In addition, the Sponsor, or designee, will be responsible for the submission of safety letters to the central IRB and to the Investigator of all SUSARs involving the active study drug according to applicable regulations. For clinical sites

Study Number: ONO-7475-01 Protocol	Version: 10.0 [incorporating Amendments #1–9]
--	--

that use a local IRB, it is the responsibility of the Investigator to promptly notify the local IRB of all SUSARs involving risk to human patients.

These reports should be submitted within 7 calendar days of the Sponsor being notified of the event for fatal or life-threatening events, or 15 calendar days for all other events.

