9.2.4 Reference Safety Information

The Sponsor or designee is responsible for determining the expectedness of the reported event(s) as per the applicable Reference Safety Information. The Reference Safety Information is contained in the IB for ONO-7475²⁵ and in the approved Product Labelling for venetoclax (VENCLEXTA)²².

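### Part D's two causality classes in section 9.1.2 do not separate events with more than one plausible cause: no reading makes a well-timed event that AML plausibly explains *Related* alone

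*Combined protocol and SAP*

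**What the plan says.** Section 9.1.2 asks the investigator to classify each AE against ONO-7475 and, in Part D, also against venetoclax. Part A has four classes and Part D has two.

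- Part D *Not related* has two limbs: timing that makes an association unlikely, or the condition that "underlying disease, other drugs or chemicals provide plausible explanations". Part A's *Not related/unlikely related* has the same two limbs.
- Part D *Related* lists four items: plausible timing, "The AE cannot be explained by concurrent disease or other drugs or chemicals", a positive dechallenge and a positive rechallenge. The same four items define Part A's *Definitely related*. Part A joins the last item with *and*, Part D with *or*. Nothing says which items the *or* joins.
- Part A's *Possibly related* takes a well-timed event where "The AE could also be explained by concurrent disease or other drugs or chemicals". Part D has no such class.

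Section 9.1.2 does not say whether the partner study drug is an other drug when each drug is judged in turn.

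The class is used, or may be used, in three visible places:

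- The Protocol Summary words the Part D primary safety endpoint as AEs and SAEs related to ONO-7475. Table 4 in section 2 gives the SA group's endpoint without that limit.
- Section 9.2.2 covers SAEs that arise after the reporting period and are "considered related to study drug will be reported to the Sponsor", if the investigator learns of them.
- Section 9.2.3 says that the Sponsor or its designee "will be responsible for submitting suspected, unexpected, serious adverse reactions (SUSARs) involving the study drug to the applicable regulatory authorities". Section 9.2.4 gives the Sponsor the judgement of expectedness.

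**The concern.** Section 1.2.2 describes Part D as the first use of ONO-7475 with venetoclax. In relapsed or refractory AML the disease is a possible cause of many events, and section 1.3 notes that venetoclax can cause pancytopenia. An event with more than one plausible cause is therefore a case that the scheme must handle.

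A two-class scheme can do that only if its boundary is clear. Here one class is entered as soon as another explanation is plausible, and the other lists the criteria that Part A reserves for its most certain class. Part A's class for a competing explanation has been dropped. Two sites could record the same event differently and both follow the text. A true effect of the combination could also be recorded as unrelated to either drug.

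**Working it through.** No arithmetic applies, and the plan gives no figure to reproduce. The check is a truth table built from the wording of section 9.1.2.

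**Inputs.** T = timing plausible. A = disease or another drug plausibly explains the event. D = dechallenge positive. R = rechallenge positive.

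**Rules.** Part D *Not related* = not T, or A. Part D *Related* depends on what the *or* joins, and four scopes are possible. The case of interest is a well-timed event that AML plausibly explains (T = 1, A = 1). For a first event R = 0.

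| What the *or* joins | Rule for *Related* | D = 0, R = 0 | D = 1, R = 0 | R = 1 |
|---|---|---|---|---|
| Last two items only | T and not A and (D or R) | *Not related* only | *Not related* only | *Not related* only |
| Rechallenge against the other three together | (T and not A and D) or R | *Not related* only | *Not related* only | both |
| Timing plus any one other item | T and (not A or D or R) | *Not related* only | both | both |
| The whole list | T or not A or D or R | both | both | both |

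With A = 1, *Not related* is met in every cell. *Related* alone is therefore impossible whatever the scope of the *or*.

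**The same event in Part A.** It meets *Not related/unlikely related* through the second limb, and also *Possibly related*. Part A overlaps too, but it gives the investigator a class that records the suspicion.

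**The two study drugs.** Assume that the partner counts as an other drug, take either of the first two scopes, and set D = 1 and R = 0.

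- AML plausible: neither drug can be *Related*.
- AML not plausible, both drugs plausible: each is the other's alternative explanation, so neither can be *Related*.
- AML not plausible, one drug plausible: that drug can be *Related*.

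If the partner is not an other drug, the second line changes and both drugs can be *Related*.

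**Side result.** A well-timed event with no other explanation and no positive dechallenge or rechallenge (T = 1, A = 0, D = 0, R = 0), such as a fatal event, meets neither Part D class on the first two scopes and is *Related* on the last two. Read literally, Part A places it in none of its four classes, so this gap is not peculiar to Part D.

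**The case against.** **The natural reading is the loosest one.** Part A's closing *and* governs all four items. Read in parallel, Part D's closing *or* does too, and the event then does meet *Related*. This stands against any claim that such events are always classed as *Not related*, or that a share of possible readings measures the problem. It does not clear the text, because on that reading the event meets both classes.

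**The phrases about other causes differ.** Part A separates an alternative that gives a plausible explanation from one that could also explain the event. This is fair. If AML is conceivable but not plausible, the second limb of *Not related* need not apply, and the list-wide *or* could leave the event as *Related* alone. The point is therefore confined to events that AML plausibly explains.

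**The partner-drug case is an assumption.** It is, and it is stated as one.

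**Recording is safe.** Section 9.1.3 records all AEs whatever the causality. Section 9.2.2 requires in-period SAEs within 24 hours regardless of relationship, and section 10.2.2.4 tabulates all treatment-emergent AEs. All of this stands. Section 9.3 also covers doubt about attribution to disease, but it decides whether an event is reported as an AE or SAE, not its causality class.

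**Dosing.** A reader might infer that venetoclax would wrongly be continued, since section 3.1.3.4 says that the Table 7 rules "should be followed in the event of each toxicity related to venetoclax during the study", and these include "Grade 3 or Grade 4 nonhematologic toxicities". The documents do not show this. That section does not cite 9.1.2, and its triggers include infection and changes merely suggestive of tumor lysis, so it does not appear to require that disease be excluded.

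**Conclusion.** The point holds as a defect in a stated rule. Part D's classes send a well-timed event that AML plausibly explains either to *Not related* alone or to both classes, depending on an *or* whose scope is not given. The conclusion rests on the visible wording of 9.1.2 and on AML being a plausible cause of the event. The extension to the two study drugs also needs the partner to count as an other drug.

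The visible consequences are limited to three:

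- the Part D primary safety endpoint, if it is reported as the Protocol Summary words it and not as in Table 4;
- SAEs after the reporting period;
- the investigator's causality input to SUSAR assessment. The Sponsor may also judge causality under processing guidelines that are not shown.

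The number of events affected cannot be estimated from the documents.

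A reader might go on to infer an effect on DLT counts, dose escalation or stopping, or a bias between Parts A and D. The documents do not support either. The DLT definitions and stopping rules are redacted and may hold their own attribution rules, and nothing visible shows how events would be classified differently in practice.

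**What to change.** Reword the Part D classes in section 9.1.2:

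- *Related*: there is a reasonable possibility that the drug caused or contributed to the event. Exclusion of disease, or a dechallenge or rechallenge result, is not required.
- *Not related*: the timing is implausible, or the event is clearly due to another cause.
- State that, for this purpose, the partner study drug is not an other drug, so that an event may be related to both.

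No change to section 3.1.3.4 or Table 7 is needed on this account. The cost is wording in one section. The downside is that more AEs will be classed as related, including some that disease caused.

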9.1.3 Adverse Event Reporting

The Investigator, or authorized designee, should regularly ask the patients how they are feeling to encourage AE reporting. The person approaching the patients should use a non-leading question such as “How are you feeling?”.

All observed or volunteered AEs, regardless of suspected causal relationship to study drug, will be recorded on the AE page(s) of the eCRF.

In addition, abnormal objective test findings (e.g., ECG changes, abnormal laboratory test results) that result in a change in the study drug dosage or in discontinuation of the drug, or require intervention or diagnostic evaluation to assess the risk to the patient, should be recorded as AEs. Clinically significant changes in physical examination findings and objective test findings should also be recorded as AEs.

Study Number: ONO-7475-01 Protocol	Version: 10.0 [incorporating Amendments #1–9]
--	--

Adverse events will be collected from the time informed consent is given until the patient has completed the study.

Any AEs that are ongoing at the time the patient completes the study will be followed by the Investigator until the AEs are resolved, the patient's condition is stable or persistent, the patient's death, or until the patient is lost to follow-up. Any pregnancies reported after completion of the study must also be reported as per Section 9.2.5.

9.2 Serious Adverse Events

9.2.1 Definition

An SAE is any untoward medical occurrence that at any dose:

- Results in death
- Is life-threatening
- Requires inpatient hospitalization or prolongation of existing hospitalization
- Results in persistent or significant disability/incapacity
- Is a congenital anomaly/birth defect
- Is medically important

Medical and scientific judgement should be exercised in deciding whether reporting is appropriate in other situations, such as important medical events that may not reach the above definition but may jeopardize the patient or may require medical or surgical intervention to prevent one of the other outcomes listed in the above definition. These events are referred to as "important medical events" and should also be considered serious. Examples of such events are the emergence of any secondary cancers unrelated to AML or MDS, intensive treatment in an accident and emergency department or at home for allergic bronchospasm, blood dyscrasias or convulsions that do not result in hospitalization, or development of drug dependency or drug abuse.

9.2.2 Serious Adverse Event Reporting by the Investigator or Designee

All SAEs, regardless of suspected relationship to study drug, must be reported by the Investigator or their authorized designee to designated service provider immediately, and in no case later than 24 hours, following knowledge of the SAE.

All SAEs are documented in the SAE form and reported electronically through the designated service provider's electronic data capture (EDC) system.

If the event meets serious criteria and it is not possible to access the EDC system, the Investigator or their authorized designee should contact the designated service provider, either by e-mail or telephone, and fax the completed paper SAE form to the designated service provider within 24 hours of awareness. The SAE

information must be entered into the EDC system within 24 hours of the system becoming available.

Safety Contact Information

[REDACTED]

[REDACTED]

[REDACTED]

[REDACTED]

[REDACTED]

The initial report of an SAE must not be delayed by the investigational site beyond 24 hours in order to collect additional information. Any medical information relevant to the reported SAE which becomes available to the investigational site staff following the initial SAE report should be reported to designated service provider as part of a follow-up SAE report. The reporting procedure should be referred to the outlined above for initial reporting of SAEs. Medical records transmitted as part of the SAE report must not disclose study patients' personal data, such as patient name, any contact information, name of patients' relatives, etc. The study patient is to be identified by the unique study-specific subject number only.

As for AEs, SAEs will be collected from the time informed consent is given until the follow-up visit, or until voluntary withdrawal of a clinical study patients' consent (refer to Section 8.3). SAEs that occur after the SAE reporting period and that are considered related to study drug will be reported to the Sponsor, if the Investigator becomes aware of them.

Unless they withdraw consent for further follow-up, patients who discontinue study therapy will be followed for acquisition of safety information through 30 days after the last dose of study treatment (or initiation of new anti-cancer therapy, whichever occurs first), and for collection of information regarding survival.

9.2.3 Serious Adverse Event Processing and Reporting by the Study Sponsor or Designee

All SAEs will be processed by the study Sponsor or contracted designee according to study-specific SAE processing guidelines.

The Sponsor, or contracted designee, will be responsible for submitting suspected, unexpected, serious adverse reactions (SUSARs) involving the study drug to the applicable regulatory authorities according to ICH guidelines and applicable regulations. In addition, the Sponsor, or designee, will be responsible for the submission of safety letters to the central IRB and to the Investigator of all SUSARs involving the active study drug according to applicable regulations. For clinical sites

Study Number: ONO-7475-01 Protocol	Version: 10.0 [incorporating Amendments #1–9]
--	--

that use a local IRB, it is the responsibility of the Investigator to promptly notify the local IRB of all SUSARs involving risk to human patients.

These reports should be submitted within 7 calendar days of the Sponsor being notified of the event for fatal or life-threatening events, or 15 calendar days for all other events.

9.2.4 Reference Safety Information

The Sponsor or designee is responsible for determining the expectedness of the reported event(s) as per the applicable Reference Safety Information. The Reference Safety Information is contained in the IB for ONO-7475²⁵ and in the approved Product Labelling for venetoclax (VENCLEXTA)²².

9.2.5 Reporting of Pregnancy

Information on pregnancy of a study patient (or partner) will be collected until the follow-up visit or until voluntary withdrawal of a clinical study patient's or partner's consent.

If the patient or female partner of a male patient participating in the study becomes pregnant during the study or within 90 days of discontinuing study drug, the Investigator should report the pregnancy to Medpace Clinical Safety within 24 hours of being notified. Medpace Clinical Safety will then forward the “Exposure *In Utero*” form to the Investigator for completion. Provided consent is obtained, the designated service provider will follow up on the outcome of all pregnancies until delivery or the end of pregnancy (i.e., delivery, still birth, miscarriage, termination), and also on the health status of the newborn. This also applies to pregnancies reported to the designated service provider after the required reporting period.

